11.4.7 Not done (ND)

FDG-PET scan not done at a given time point.

On central review, FDG-PET avid lesions will be evaluated by both the Curie scoring method and by enumeration of lesions to grade response.

11.5 Urine Catecholamines

Due to variance with diet and concomitant medications, frequently missing dopamine levels, and lack of standardized methodology for this assay, urine catecholamines will not be utilized in grading response. Results of urine catecholamines will still be requested at all response evaluation time points and recorded in database as both actual value and as "elevated" or "not elevated". Catecholamines must be at least 3 standard deviations above the mean for age to be classified as "elevated".

11.6 Definition of Overall Response for Each Patient

The criteria below will be used to define the overall response for each patient, with consideration of all three individual response parameters: CT/MRI, MIBG (FDG-PET if MIBG non-avid), and Bone Marrow.

11.6.1 Complete Response (CR)

Response of CR or NI for MIBG, (FDG-PET if tumor is not MIBG avid), CT/MRI, and bone marrow.

11.6.2 Complete Response MRD (CR-MRD)

Response of CR or NI for MIBG (FDG-PET if tumor is not MIBG avid), CT/MRI response of CR or NI, with BM response of CR-MRD

11.6.3 Partial Response (PR)

Response of PR in both CT/MRI and MIBG (FDG-PET if tumor is not MIBG avid); or response of PR in either CT/MRI or MIBG (FDG-PET if tumor is not MIBG avid) with response of CR, NI, or SD-NTL for other parameter. Bone marrow response of either CR, CR-MRD, NI, or SD for patients with maximum amount of tumor \leq 5% at baseline.

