11.2.4 Stable Disease (SD)

Stable disease will be defined as persistence of an amount of tumor in the bone marrow that does not meet criteria for progressive disease or CR or CR- Minimal Residual Disease. (Note that patients who enter with $\leq 5\%$ tumor and have one negative bone marrow which is initially graded as a CR-MRD and then on subsequent time points have 1-10% tumor noted would be then considered as SD at all time points, including the time point initially graded as CR).

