If a solitary soft tissue lesion extends into both the chest and abdomen/pelvic regions, score 3 for that lesion. For example, a large paraspinous mass that extends along the thoracic and lumbar spine would be scored a 3 for Region 10. Any corresponding metastatic bone disease within the thoracic or lumbar spine would be scored separately for the cervico-thoracic spine (Region 2) and lumbar spine (Region 4).

Conjugate planar imaging will be used to score a given region. SPECT scans may be used as an adjunct, but only to help delineate the location of the MIBG avid lesion.

The **relative score** is calculated by dividing the absolute score at each time by the corresponding pre-treatment overall score. The relative score of each patient is calculated at each response assessment and classified as below:

- a. Complete response: all areas of uptake on MIBG scan completely resolved.
- b. Partial response: Relative score ≥ 0.1 to ≤ 0.5
- c. Stable disease: Relative score > 0.5 to < 1.2
- d. Progressive disease: New lesions on MIBG scan OR a relative score ≥ 1.2 . Biopsy of new lesions may be done to rule out progressive disease. If biopsy is negative for tumor (neuroblastoma and/or ganglioneuroblastoma), patient will not meet definition of PD.
- e. Not evaluable (NE): MIBG scan of inadequate quality as assessed by central reviewer.
- f. Not involved (NI): No MIBG avid lesions at study entry and subsequent response time points.
- g. Not done (ND): MIBG scan not done at a given response time point

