11.6.5 Stable disease (SD)

Response of stable disease for at least one parameter, with response of SD, NI, or SD-NTL for other parameters.

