11.6.6 Minor response (MR)

Complete response, Complete-MRD response, and/or partial response for one parameter (i.e. CT/MRI, MIBG (FDG-PET if MIBG non-avid), bone marrow), with response of stable disease for second parameter and any response other than PD or not evaluable for third parameter.

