11.6.10 Summary

The overall response as assessed at any particular time point based on consideration of each of the three parameters as defined above is summarized in the following table:

Overall Response Assignment

CT/MRI Response	MIBG Response*	Bone Marrow Response	Overall Response
	PD for any one parameter with any response (including Not Evaluable or Not Done) for the other 2 parameters. PD may also be defined by clinical assessment of the treating physician only.		PD
CR	CR	CR	CR
CR for one parameter with either CR or NI for other parameters			CR
MIBG response = CR or NI CT/MRI response = CR or SD-NTL or NI		CR-MRD	CR-MRD
CR or PR or SD-NTL or NI	PR	CR or CR-MRD or NI -OR- SD if ≤ 5% tumor in bone marrow at study entry	PR
PR	CR or PR or NI	CR or CR-MRD or NI -OR- SD if ≤ 5% tumor in bone marrow at study entry	PR
SD for one parameter, with SD or NI or SD-NTL for other two parameters			SD
CR or CR-MRD or PR for at least one parameter, SD for a second parameter, and any response other than PD or Not Evaluable for other parameter			Minor response
Response of Not Evaluable for any one of the 3 parameters that had measurable/evaluable tumor at study enrollment and no PD for any parameter.			Not Evaluable
No response evaluations performed for any of the 3 parameters			Not Done
NI or non-target lesions only at enrollment and no PD on subsequent timepoint	NI at enrollment and no PD at subsequent time point	NI at enrollment and no PD at subsequent time point	No progression

*For patients who utilize FDG-PET in place of MIBG response, then substitute FDG-PET response for MIBG response in this table to define overall response.

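### The version 1.2 overall-response rules can grade a deeper imaging response below a shallower one, and leave some response patterns without a grade

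*Combined protocol and SAP*

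**What the plan says.** Section 11.0 applies version 1.2 to all patients at central review, and central review defines response for the final analysis. Overall response combines CT/MRI, MIBG (FDG-PET if the tumor is not MIBG avid) and bone marrow.

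- Overall CR (11.6.1): CR or not involved (NI) in all three.
- Overall CR with minimal residual disease, CR-MRD (11.6.2): MIBG CR or NI and "CT/MRI response of CR or NI, with BM response of CR-MRD". The table in 11.6.10 is wider: "MIBG response = CR or NI CT/MRI response = CR or SD-NTL or NI".
- Overall PR (11.6.3): "Response of PR in both CT/MRI and MIBG (FDG-PET if tumor is not MIBG avid); or response of PR in either CT/MRI or MIBG", where the other imaging parameter may be CR, NI or SD-NTL. Marrow may be CR, CR-MRD, NI, or SD if baseline tumor was at most 5%.
- Minor response (11.6.6): CR, CR-MRD or PR in one parameter, "with response of stable disease for second parameter and any response other than PD or not evaluable for third parameter".
- Overall SD (11.6.5): SD in at least one parameter, "with response of SD, NI, or SD-NTL for other parameters".
- MIBG grades (11.3): "Complete response: all areas of uptake on MIBG scan completely resolved"; PR from 0.1 to 0.5 inclusive; "Stable disease: Relative score > 0.5 to < 1.2". New lesions, or a score of 1.2 or more, are progression.

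Section 10.2.2 counts its groups a to c (complete, very good partial and partial response) as responders. It names neither CR-MRD nor Minor response.

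**The concern.** A response scale should be monotone: improving one parameter and leaving the others alone should never lower the overall grade. It should also give every assessable patient a grade. Section 11.6.3 asks for a PR on imaging and does not say that a CR serves as well. That is harmless where overall CR picks up the better case, but overall CR excludes marrow SD and SD-NTL. A patient whose imaging clears, but whose marrow stays at a low level, can therefore pass from responder to non-responder because the imaging result was better.

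Central reviewers would have to follow an order that makes no clinical sense, or improvise after seeing the scans. Either way, the primary endpoint is not fully fixed in advance.

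**Working it through.** **The plan's own figure.** Section 10.4 gives a 90% chance of at least 1 response in 14 at a true rate of 15%. 1 − 0.85^14 = 0.897, so it reproduces. The documents give no figure for how often each response pattern occurs.

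**Grid.** Sections 11.6.1 to 11.6.8 were applied to CT/MRI {CR, PR, SD, SD-NTL, NI} × MIBG {CR, PR, SD, NI} × marrow {CR, CR-MRD, SD from ≤5%, SD from >5%, NI}. That is 5 × 4 × 5 = 100 combinations, or 99 without all-NI. Progression, Not Evaluable and Not Done were left out. Patterns are written CT/MIBG.

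**Two conventions the text leaves unwritten.**

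- CR and PR are exclusive grades, because 11.6.3 and the table list them separately.
- PR takes precedence over Minor response. Six PR cells have marrow SD from ≤5%: PR/PR, PR/CR, PR/NI, CR/PR, NI/PR and SD-NTL/PR. All six also meet the Minor rule, so without this precedence the ≤5% clause in 11.6.3 would never operate.

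**Inversions, marrow SD from ≤5%.**

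| CT/MIBG | Grade | With PR in place of a CR | Grade |
|---|---|---|---|
| CR/CR | Minor | PR/CR or CR/PR | PR |
| CR/NI | Minor | PR/NI | PR |
| NI/CR | Minor | NI/PR | PR |
| SD-NTL/CR | Minor | SD-NTL/PR | PR |

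**SD-NTL.** Section 11.6.5 lists SD-NTL apart from SD.

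- Kept separate: SD-NTL/CR with marrow CR or NI, and SD-NTL/NI with marrow CR, fit no rule. That is 3 cells under the table. The text of 11.6.2 adds SD-NTL/CR and SD-NTL/NI with marrow CR-MRD, making 5.
- Read as SD: no cell is ungraded. But SD-NTL/CR with marrow CR or NI becomes Minor, while SD-NTL/PR with the same marrow is PR. Inversions rise from 4 to 6 (table). Under the text, SD-NTL/CR with marrow CR-MRD makes 7.

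**MIBG gap.** Ten regions scored 0 to 3 give a range of 0 to 30. The ungraded zone is 0 < residual/baseline < 0.1 without new lesions.

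- Residual 1 needs a baseline of 11 to 30: 20 pairs. For example, 1/11 = 0.091.
- Residual 2 needs a baseline of 21 to 30: 10 pairs.
- Residual 3 would need a baseline above 30: none.

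The total is 30 score pairs, and the baseline must be at least 11.

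**Effect of letting CR serve where 11.6.3 asks for PR.** Counting CR, CR-MRD and PR as response, responder cells go from 37 to 43 under the table (6 added) and from 35 to 42 under the text (7 added). No responder cell is lost. SD-NTL/NI with marrow CR still has no grade under either source if SD-NTL is separate, nor does SD-NTL/NI with marrow CR-MRD under the text.

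**Per patient.** 1/20 = 5 points on the response rate. The stage 1 decision changes only if the affected patient would be the sole responder among 14.

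**The case against.** The strongest reply is that grades may be nested. A CT CR also satisfies a decrease of at least 30%, and full FDG-PET resolution also satisfies a reduction of at least 50%. On that reading CR/CR and CR/NI with marrow SD from ≤5% are overall PR, and with FDG-PET so are NI/CR and SD-NTL/CR. So four inversions should not be taken as the count under every reading. The nested reading is disfavored, because 11.6.3 and the table treat CR and PR as different grades. It also fails for MIBG, where PR has a floor of 0.1: NI/CR and SD-NTL/CR stay inverted.

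Likewise, the ungraded SD-NTL cells are not a settled fact. Section 11.1.4.5 names SD-NTL as a kind of stable disease. That reading removes the gaps but adds inversions.

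Other points stand as limits:

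- A near-zero MIBG score would plausibly be called CR or PR, and either usually leads to a responder.
- The cell totals count CR-MRD as response, although 10.2.2 does not name it. Counting only CR and PR, the literal table has 7 + 24 = 31 responder cells.
- Best response (10.6.2) rescues anyone graded as a responder at another evaluation. It does not rescue a marrow CR-MRD in a patient whose later marrow shows 1–10% tumor: under 11.2.4 such patients "would be then considered as SD at all time points, including the time point initially graded as CR", and an overall CR-MRD with imaging CR then becomes Minor.
- Phase 2 has no final success threshold beyond the stage 1 rule, only a confidence interval.

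A reader might infer that the 90% stage 1 figure is too high, or that the response rate is biased low against the 15% benchmark. The documents do not support either, since they give no frequency for these patterns.

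**Conclusion.** The defect is real, in a rule that the primary endpoint uses. With exclusive grades and PR ahead of Minor response, four patterns with marrow SD from ≤5% make a better imaging result a non-response. No reading examined clears the MIBG-graded patterns NI/CR and SD-NTL/CR. On SD-NTL, the plan has either ungraded cells (3 by table, 5 by text) or more inversions (6 by table, 7 by text). The MIBG gap, the disagreement between 11.6.2 and the table, and the outdated responder list in 10.2.2 are separate and do not depend on those conventions.

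Cell counts are not patient shares. The number of patients affected is unknown and probably small, many would be rescued by best response, and no net bias is claimed. The wording should be corrected because this is cheap and because a single patient is 5 points at n = 20.

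**What to change.** Settle the following before central review results are seen:

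- (a) In 11.3, define MIBG PR as residual uptake with a relative score above 0 and up to 0.5, and no new lesions.
- (b) In 11.6.3 and the 11.6.10 table, define overall PR as PR or CR in CT/MRI or MIBG; the other imaging parameter PR, CR, NI or SD-NTL; marrow CR, CR-MRD, NI or SD from ≤5%; and overall CR and CR-MRD not met. State that PR takes precedence over Minor response.
- (c) Reconcile 11.6.2 with the table on SD-NTL so that, with the same imaging, marrow CR never ranks below marrow CR-MRD. Keeping the table's CR-MRD row next to (b) would not achieve this: SD-NTL/CR would be PR with marrow CR but CR-MRD with marrow CR-MRD. Have the study committee assign a grade to SD-NTL/NI with marrow CR (and with marrow CR-MRD if the text of 11.6.2 is kept). This is a choice, since neither imaging parameter responds.
- (d) In 10.2.2, name CR, CR-MRD and PR as responders and Minor response as non-responder.
- (e) Report the response rate under both the literal and the corrected rules, with the primary one named in advance.

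The cost is wording applied at a central review already planned, with no extra scans or patients. There are two downsides. It departs slightly from the network-wide version 1.2 wording, which Amendment 6 adopted for uniformity. And it is a mid-trial clarification that can only add responders, provided (c) does not withdraw a responder grade the table now gives. Reporting both rates makes that visible.

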11.6.4 Progressive Disease (PD)

Either one of the following will define an overall response of PD:

- a. At least one response parameter including CT/MRI, MIBG, bone marrow and/or FDG-PET response is PD. If PD is found by one parameter, the other two parameters are not required to be evaluated to define an overall response of PD.
- b. Treating physician grades patient as progressive disease based on clinical assessment without radiographic or bone marrow evaluations.

11.6.5 Stable disease (SD)

Response of stable disease for at least one parameter, with response of SD, NI, or SD-NTL for other parameters.

11.6.6 Minor response (MR)

Complete response, Complete-MRD response, and/or partial response for one parameter (i.e. CT/MRI, MIBG (FDG-PET if MIBG non-avid), bone marrow), with response of stable disease for second parameter and any response other than PD or not evaluable for third parameter.

11.6.7 Not evaluable (NE)

Response of Not evaluable for one or more response parameters including CT/MRI, MIBG (FDG-PET if MIBG non-avid), or bone marrow for any parameter that had measurable/evaluable tumor at study enrollment. However, if one parameter is done and demonstrates PD this is defined as an overall response of PD. In addition, response may be declared not evaluable if review by the Study Management Committee / PI deems that there is insufficient data to grade response.

11.6.8 No progression

Baseline status at enrollment was NI or non-target lesions only for CT, NI for bone marrow, NI for MIBG (FDG-PET if MIBG non-avid) and there has NOT been PD at any site since on protocol therapy

11.6.9 Not done (ND)

Response not assessed at this time point.

11.6.10 Summary

The overall response as assessed at any particular time point based on consideration of each of the three parameters as defined above is summarized in the following table:

Overall Response Assignment

CT/MRI Response	MIBG Response*	Bone Marrow Response	Overall Response
	PD for any one parameter with any response (including Not Evaluable or Not Done) for the other 2 parameters. PD may also be defined by clinical assessment of the treating physician only.		PD
CR	CR	CR	CR
CR for one parameter with either CR or NI for other parameters			CR
MIBG response = CR or NI CT/MRI response = CR or SD-NTL or NI		CR-MRD	CR-MRD
CR or PR or SD-NTL or NI	PR	CR or CR-MRD or NI -OR- SD if ≤ 5% tumor in bone marrow at study entry	PR
PR	CR or PR or NI	CR or CR-MRD or NI -OR- SD if ≤ 5% tumor in bone marrow at study entry	PR
SD for one parameter, with SD or NI or SD-NTL for other two parameters			SD
CR or CR-MRD or PR for at least one parameter, SD for a second parameter, and any response other than PD or Not Evaluable for other parameter			Minor response
Response of Not Evaluable for any one of the 3 parameters that had measurable/evaluable tumor at study enrollment and no PD for any parameter.			Not Evaluable
No response evaluations performed for any of the 3 parameters			Not Done
NI or non-target lesions only at enrollment and no PD on subsequent timepoint	NI at enrollment and no PD at subsequent time point	NI at enrollment and no PD at subsequent time point	No progression

*For patients who utilize FDG-PET in place of MIBG response, then substitute FDG-PET response for MIBG response in this table to define overall response.

12.0 ADVERSE EVENT REPORTING REQUIREMENTS

Rapid mandatory toxicity case report and hemogram forms will be submitted to the NANT Operations Office weekly for all patients on Course 1.

12.1 Purpose

Adverse event data collection and reporting, which are required as part of every clinical trial, are done to ensure the safety of patients enrolled in the studies as well as those who will enroll in future studies using similar agents. Adverse events are reported in a routine manner at scheduled times during a trial. (Please follow directions for routine reporting provided in the data collection packet for this protocol). Additionally, certain adverse events must be reported in an expedited manner to allow for timelier monitoring of patient safety and care. The following sections provide information about expedited reporting through the use of a written IND safety report (MedWatch) to the Food and Drug Administration (FDA).

Adverse events will be graded according to the NCI Common Terminology Criteria for Adverse Events (CTCAE), Version 4. A copy of the CTCAEv4 can be downloaded from the CTEP home page (<http://ctep.cancer.gov>).

12.2 Definitions

Adverse Event (AE): An adverse event means any untoward medical occurrence associated with the use of a drug in humans, whether or not considered drug related.

Suspected Adverse Reaction: Any adverse event for which there is a reasonable possibility that the drug caused the adverse event. Reasonable possibility means there is evidence to suggest a causal relationship between the drug and the adverse event.

Unexpected Adverse Event or Unexpected Suspected Adverse Reaction: An adverse event or suspected adverse reaction is considered “unexpected” if it is not listed in the investigator brochure or is not listed at the specificity or severity that has been observed; or, if an investigator brochure is not available, is not consistent with the risk information described in the general investigational plan.

Serious Adverse Events (SAE) or Serious Suspected Adverse Reactions: An adverse event or suspected adverse reaction is considered serious if, in the view of either the investigator or sponsor, it results in any of the following outcomes:

Death of Patient	An event that results in the death of a patient.
Life-Threatening	An event that, in the opinion of the investigator, would have resulted in immediate fatality if medical intervention had not been taken. This does not include an event that would have been fatal if it had occurred in a more severe form.
Hospitalization	An event that results in an admission to the hospital for any length of time. This does not include an emergency room visit or admission to an outpatient facility.
Prolongation of Hospitalization	An event that occurs while the study patient is hospitalized and prolongs the patient's hospital stay.
Congenital Anomaly	An anomaly detected at or after birth or any anomaly that result in fetal loss.
Persistent or Significant Disability/ Incapacity	An event that results in a condition that substantially interferes with the activities of daily living of a study patient. Disability is not intended to include experiences of relatively minor medical significance such as headache, nausea, vomiting, diarrhea, influenza, or accidental trauma (e.g., sprained ankle).

Important Medical Event Requiring Medical or Surgical Intervention to Prevent Serious Outcome	An important medical event that may not be immediately life-threatening or result in death or hospitalization, but based on medical judgment may jeopardize the patient and may require medical or surgical intervention to prevent any of the outcomes listed above (i.e., death of patient, life-threatening, hospitalization, prolongation of hospitalization, congenital anomaly, or persistent or significant disability/incapacity). Examples of such events include allergic bronchospasm requiring intensive treatment in an emergency room or at home, blood dyscrasias or convulsions that do not result in inpatient hospitalization, or the development of drug dependency or drug abuse.
--	--

12.3 Expedited Serious Adverse Event Reporting to NANT Operations

For any serious adverse event, both **expected and unexpected**:

- Contact the Study Chairperson and the NANT Operations Center to alert them to the existence of the serious adverse event within 24 hours of learning of the event
- Within 48 hours of learning of the event complete the NANT SAE form (see NANT website www.nant.org under protocol data forms/generic forms packet) and email to [contact].
- Follow-up information should be submitted as soon as relevant information is available.

Copies of all serious adverse event reports will be kept on file in the NANT Operations Center. All NANT institutions are to file SAE reports with their Institutional Review Boards according to local institutional policy.

12.4 Expedited Adverse Event Reporting to the FDA

Per CFR 312.32 (c), the sponsor of the IND, [name], must notify the FDA and all participating investigators in a written IND safety report of any adverse experience **associated with use of the drug** that is **both serious and unexpected**. Each written notification shall be made as soon as possible, and in no event later than **15 calendar** days after the sponsor's initial receipt of the information. Each written notification may be submitted on FDA Form 3500A (MedWatch) or in a narrative format and must bear prominent identification of its contents, i.e., "IND Safety Report". Follow-up information to a safety report should be submitted as soon as the relevant information is available.

The sponsor must also notify FDA **by telephone** or by **facsimile** transmission of any **unexpected fatal or life-threatening experience associated with use of the drug** in the clinical studies conducted under the IND as soon as possible but in no event later than **7 calendar** days after initial receipt of the information.

Each telephone call or facsimile transmission to the FDA shall be transmitted to the FDA division that has responsibility for review of the IND; a specific contact person is assigned to each IND at the time the application is filed, and this will be included in the FDA's correspondence acknowledging receipt of the IND application.

12.5 NANT Operations Center Role in Expedited Adverse Event Reporting to the FDA and Participating Sites

For purposes of this protocol, the MedWatch Report Form (FDA 3500A) will be submitted to the FDA by NANT on behalf of the IND sponsor, [name]. These forms will be submitted to the appropriate FDA division and will serve as the written IND safety report. The NANT Operations Center will file all expedited adverse event reports as well as other adverse events with the FDA and other relevant authorities or investigators. The IND sponsor, [name], has also delegated to the NANT Operations Center the telephone/facsimile FDA notification responsibilities for unexpected fatal or life-threatening experiences. All IND submissions will be maintained in a master file at the NANT Operations Center.

For Adverse Events associated with the use of the drug that are both Serious and Unexpected:

- The MedWatch form will be drafted by the NANT Operations Center based on the SAE form within 10 days of the adverse event and reviewed with PI at treating site and the study chair. Final Medwatch form will be submitted to FDA by NANT Operations Center. Electronic version of MedWatch form is available from NANT Operations Center or Med Watch website www.fda.gov/medwatch. NANT will forward the completed report the FDA and other relevant authorities or investigators on behalf of the IND Sponsor, [name].
- Follow-up information should be submitted as soon as relevant information is available.

For Adverse Events associated with the use of the drug that are Unexpected or Life Threatening:

- Notify the NANT Operations Center (who will notify the FDA and other relevant authorities and investigators) by telephone or fax as soon as possible but no later than 7 calendar days from the occurrence of the event.

FDA [contact]

FDA [contact]

- The MedWatch form will be drafted by the NANT Operations Center based on the SAE form within 10 days of the adverse event and reviewed with PI at treating site and the study chair. Final Medwatch form will be submitted to FDA and other relevant authorities or investigators by NANT Operations Center on behalf of the IND Sponsor, [name].
- Follow-up information should be submitted as soon as relevant information is available.

A cover letter to accompany the Med Watch report will be prepared by the NANT Operations Center in collaboration with the IND sponsor, [name]. Cover letter will be submitted with MedWatch report to the FDA and other NANT institutions and relevant authorities). Contents will include:

1. An assessment of the adverse event and its significance/relevance to the study. Does the occurrence of this AE alter the risk/benefit ratio of the study.
2. A statement as to whether this adverse event has been reported previously, and if so, whether the frequency is considered unusually high.
3. A statement as to whether the informed consent should reflect changes in the potential risks involved.

Copies of all adverse event reports will be kept on file in the NANT Operations Center. All NANT institutions are to file AE reports with their Institutional Review Boards according to local institutional policy. The NANT Operations Center will also distribute copies of AE reports to Millennium Pharmaceuticals Inc within two working days.

